122 the 24 to 72 hours following the initiation of therapy with IDeg (10). There is
123 currently no evidence-based guidance on how to minimize glucose excursions when
124 transitioning patients from their existing basal insulin to IDeg. The package insert for
125 IDeg suggests a 1:1 dose conversion from other basal insulin regimens to IDeg for
126 adult patients. However, this does not account for the time it takes IDeg to achieve
127 steady state and can result in worsening of glycemic control in the 48-72 hours after
128 the transition is made. Many practitioners at the University of Washington Diabetes
129 Clinic have seen better glycemic control within the first 12 to 24 hours in T1D
130 patients in whom we gave 50% of their usual dose of insulin glargine at bedtime
131 along with the first dose of IDeg. This leads to our hypothesis that a bridging therapy
132 involving the use of a reduced amount of patients' prior basal insulin at the time of
133 initiating IDeg will lead to improved glycemic control in the first 24-72 hours on
134 IDeg, minimizing the morbidities associated with hyperglycemia and the need for
135 correctional insulin and also avoiding hypoglycemia resulting from over-correction
136 due to use of additional rapid-acting insulin. Additionally, we will follow what has
137 been done in prior clinical trials of conversion from other basal insulins to IDeg and
138 hence, convert them from their insulin glargine total daily dose to 80% of that dose
139 as IDeg (4). An improvement in the safety and ease of transitioning from the more
140 commonly used glargine to IDeg may greatly encourage more providers and patients
141 to adopt IDeg as the basal insulin of their choice. Another benefit would be knowing
142 how to transition patients back to their outpatient IDeg therapy when they are being
143 discharged home from an inpatient stay and were switched to insulin glargine during
144 their hospitalization, as IDeg is not formulary in many hospitals. The purpose of this
145 pilot study is to gain preliminary evidence of whether bridging with insulin glargine
146 while transitioning to IDeg provides better glycemic results in the transition period
147 compared to direct conversion.

148148

149 2. ENDPOINTS AND OBJECTIVES:

150 Primary endpoint:

151 Change in percent time spent in target glycemic range (TIR, glucose 70-180 mg/dL, both
152 values included) in the 48 hours before and the 48 hours after the 1st dose of IDeg

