153 Primary objective:

154 To compare the mean change in percent time in range (as defined by the primary
155 endpoint) between patients who transition directly to IDeg to the mean change in patients
156 who use a bridging dose of insulin glargine along with 1st dose of IDeg.

157

158 Secondary end points:

159 These will include the following data obtained from their CGM download in the 48 hours
160 following the first dose of IDeg as measured as a difference compared to the 48 hours
161 preceding the dose:

- 162 1. Coefficient of variation of percent-time-in-range for each treatment within
163 each group
- 164 2. Nocturnal time in range of 70-180 mg/dL (between mid-night and 0600 hours,
165 both values included)
- 166 3. Percent time above 180 mg/dL (TAR-1), percent time above 250 mg/dL
167 (TAR-2) for each treatment within each group
- 168 4. Percent time below 70 mg/dL (TBR-1), percent time below 54 mg/dL (TBR-
169 2) for each treatment within each group
- 170 5. Number of correction boluses for each treatment within each group

171

172 Secondary objectives:

173 To compare each of the secondary endpoints between patients who use a bridging dose to
174 patients who transition directly to IDeg.

175

176 3. RESEARCH DESIGN AND METHODS

177 3.1 **Study Hypothesis:**

178 Our hypothesis is that among patients who transition from insulin glargine to IDeg, those
179 who use a bridging dose of insulin glargine will not have a significant change, on average,
180 in time spent in target glycemic range during the transition period, whereas, those
181 transitioning directly to IDeg will have a significant change in this parameter. We further
182 hypothesize that those using the bridging dose of insulin glargine will have less
183 hypoglycemia, less hyperglycemia and need fewer correction boluses than the direct-
184 conversion patients during the transition period.

185 3.2 **Study type:**

186186

187 This will be a double-blind, randomized, single-center, proof-of-concept study.
188 Randomization will be stratified by use of insulin glargine once daily or twice daily at
189 baseline. Randomization will be conducted using permuted-block design with a block
190 size of 4, ensuring equal numbers of bridging and non-bridging patients in each of the 2

191 resultant strata after every 4th patient is randomized within a stratum. The 2 strata with
192 blocked randomization within each stratum will result in 4 groups as follows:

193 **1. Bridging Groups:**

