402 instructed to keep the study CGM on at all times for this duration. If they have their own
403 CGM, then they will be allowed to keep that on in addition to the study CGM, should
404 they desire to do so. They will be instructed to replace the sensor, if needed. The study
405 CGM insertion day will be considered day 0. The next day will be day 1. Transition to
406 IDeg will be done on Day 3 as below. Subjects will be dispensed a log book in which
407 they will need to document carbohydrates consumed, exercise duration and time, timing
408 and doses of basal and bolus insulin (broken down as prandial and correction), self-
409 monitored blood glucose values, hypoglycemia symptoms and intervention for each day
410 they are in the study (from CGM insertion to removal) (See Appendix A and B). We will
411 inquire about any change to concomitant medications and document insulin doses being
412 administered.

413

414

415 **3.10.2.1 Insulin Dosing:**

416 At visit 2, subjects will also be given written instructions on how to do the transition from
417 insulin glargine to IDeg.

418

419 *Calculation of IDeg dose*

420 The dose of IDeg that subjects will be switched to will equal 80% of the total daily dose
421 of insulin glargine they reported using at visit 1. This reduction is what was done in the
422 clinical trials of conversion from any basal insulin to IDeg with lower risk of
423 hypoglycemia (4). For example, if a subject was on 25 units of glargine at screening visit,
424 then they will need to switch to 20 units of IDeg ($0.8 \times 25 = 20$). Number of units will be
425 rounded up to the next whole number if decimal points are ≥ 0.5 and rounded down if
426 <0.5 .

427

428 *Timing of IDeg dose*

429 To keep things consistent across participants, we will instruct all patients to start their
430 first dose of IDeg 3 days after the study CGM is inserted. The rationale for this is that the
431 first 24 hours of data on the CGM is not very accurate and after that we want 48 hours of
432 baseline glucose data on insulin glargine, prior to transitioning to IDeg. This will be used
433 later as their baseline to compare with the values seen on IDeg. Subjects will be
434 instructed to administer their first dose of IDeg at 2100 hours on the 3rd day after
435 insertion of study CGM. They will then administer the same dose of IDeg every night for
436 5 ± 2 consecutive doses.

437

438 *Dosing of Insulin Glargine*

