606 Compliance will be defined by the following (all 3 need to be met to be considered 607
607 compliant), assessed during the 48 hours prior to and after the first dose of IDeg:
611
612

- 608 • No missed doses of basal insulin
- 609 • No missed doses of nutritional insulin with meals
- 610 • Wearing the study CGM for >19 hours a day

613 4. STATISTICAL CONSIDERATIONS:

614 The primary objective of this pilot study is to calculate the change in percent time that 615 BG is “in range” (TIR defined as 70-180 mg/dL) in the 48 hours before the first IDeg 616 dose vs. the 48 hours after the first dose, and to compare the mean of this change between 617 patients who are randomized to receive bridging glargine and those who are randomized 618 to not receive bridging glargine. Randomization will be stratified by glargine use (once 619 vs. twice daily). For each patient, the TIR in the 48 hours before first IDeg use will be 620 calculated, as will the TIR in the 48 hours after first IDeg use. The difference of these 621 values will then be calculated, and the mean of the differences compared between the 622 randomized arms. Our primary hypothesis will assume that the “bridging effect” is 623 similar between patients who take glargine once daily and twice daily. However, we plan 624 an exploratory look at this assumption as a secondary objective.

625

626 If we assume the true change in TIR (before first dose of IDeg minus after first dose of 627 IDeg) to be 0% for the bridging group and 15% for the non-bridging group, and if we 628 assume a common standard deviation of 15% (meaning the distributions of change in TIR 629 are separated by 1 standard-deviation unit), then 20 patients in each group will provide 630 87% power to observe a statistically significant (at the two-sided level of .05) difference 631 in mean change of TIR.

632

633 As noted above, we’ll assess the magnitude of this difference as a function of once- vs. 634 twice-daily glargine use. With only 40 patients, it’s highly unlikely that a statistically 635 significant interaction will be observed, but if the directions of the difference in mean 636 changes are the same in the once-daily vs. twice-daily groups we shall consider the 637 results to be consistent with each other.

638

639 Secondary endpoints to be assessed in a descriptive manner include the following:

- 640 1. Coefficient of variation of TIR for each treatment within each group

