- 641 2. Nocturnal time in range of 70-180 mg/dL (nTIR; both values included) (between
- 642 mid-night and 0600 hours)
- 643 3. Percent time above 180 mg/dL (TAR-1), percent time above 250 mg/dL (TAR-2)
- 644 for each treatment within each group
- 645 4. Percent time below 70 mg/dL (TBR-1), percent time below 54 mg/dL (TBR-2)
- 646 for each treatment within each group
- 647 5. Number of correction boluses for each treatment within each group

648

649 The overarching goal of this pilot study is to collect data in a controlled setting on a 650 variety of long-acting insulin regimens and gain an idea if there is a signal. The data 651 generated in this pilot study will be used to assist in the design of a future and larger 652 study where a more definitive comparison of efficacy will be conducted.

653

654

655 5. DATA HANDLING AND RECORD KEEPING:

656 Study information will be collected for each participant by research staff using 657 standardized Case xReport Forms (CRFs). CRFs will not report information about

658 treatment assignment in order to maintain blinding of treatment allocation. Forms will be 659 stored at a secure location at the clinical site. We expect that the majority of data will be 660 collected via CRFs; however, other data sources, such as CGM download and laboratory 661 data, may be used. All study data will be entered into the Research Electronic Data 662 Capture (REDCap), a web-based data entry and management system that is HIPPA 663 compliant and powered by the Institute of Translational Health Sciences, by research 664 staff. The clinical data management procedures will be consistent with the International 665 Conference on Harmonisation (ICH E6) standards for Good Clinical Practice (GCPs)¹.

666

667

668 6. ETHICS:

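### The primary comparison of TIR change omits baseline TIR and the randomisation stratum; the test is valid, but naming both in the model is a cheap way to gain precision

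*Combined protocol and SAP*

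**What the plan says.** - **Endpoint (Section 2).** Change in percent TIR ("values included) in the 48 hours before and the 48 hours after the 1st dose of IDeg").
- **Primary analysis (Section 4).** TIR is calculated for each patient in each window. The difference of these "values will then be calculated, and the mean of the differences compared between the" randomised arms. No test, model or covariate is named.
- **Power (Section 4).** The true change is taken "IDeg) to be 0% for the bridging group and 15% for the non-bridging group, and if we" "assume a common standard deviation of 15% (meaning the distributions of change in TIR" are one SD apart). With 20 per group this is said to give 87% power at two-sided 0.05.
- **Stratification (Section 3.2; also Sections 4 and 8.5).** "Randomization will be stratified by use of insulin glargine once daily or twice daily at" baseline, in permuted blocks of 4, 1:1 within stratum.
- **Use of the stratum in the analysis (Section 4).** Exploratory only. The plan will "assess the magnitude of this difference as a function of once- vs" twice-daily use, and will call the two strata consistent if the differences point the same way.
- **Baseline data (Section 3.10.2.1).** The run-in is set up to give 48 hours of "baseline glucose data on insulin glargine, prior to transitioning to IDeg. This will be used" as the comparator for values on degludec.

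No other section adds an adjusted model.

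**The concern.** Subtracting after from before fixes the slope of post-dose TIR on baseline TIR at 1. If the true slope differs, the change score still carries variation that baseline TIR could remove. Likewise, stratifying the randomisation balances glargine frequency between arms, but an analysis without the stratum leaves between-stratum variation in the standard error. If the stratum predicts the change, the interval is then too wide and the test conservative.

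What is at stake is precision. Section 4 describes a pilot meant to collect data on a "variety of long-acting insulin regimens and gain an idea if there is a signal. The data" are then to inform a larger study. With 40 patients, the width of the interval around the arm difference is much of what the pilot delivers.

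**Working it through.** **1. Reproduce the stated power.** Inputs from Section 4: effect 15, SD of change 15, 20 per arm, two-sided 0.05.

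- Noncentrality = 15 / (15 × √(2/20)) = 3.162. With 38 df the two-sample t-test has power 86.9%, which matches 87%. The normal approximation gives 88.5%.
- 95% CI half-width = 2.024 × 15 × √(2/20) = 9.60 points.

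The stated power is therefore that of an unadjusted comparison of change scores.

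**2. What baseline adjustment can remove.** Let ρ be the before/after TIR correlation and k the ratio of after-SD to before-SD. Neither is in the documents. The ratio of residual variance to change variance is

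k²(1 − ρ²) / (1 + k² − 2ρk).

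At k = 1 this is (1 + ρ)/2. At ρk = 1 it equals 1, so there is nothing to gain. Example at k = 1, ρ = 0.5: ratio 0.75, residual SD 15 × √0.75 = 12.99, half-width 2.028 × 12.99 × √(2/20) = 8.33. Chance baseline imbalance raises this to about 8.4.

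**3. Power with baseline and stratum in the model.** Simulation of 40,000 trials per scenario, 40 patients, strata split 24/16, stratum not prognostic, SD of change held at 15. Entries are unadjusted → adjusted power (%).

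| ρ | k = 1 | k = 1.25 | k = 1.5 |
|---|---|---|---|
| 0.3 | 87.0 → 96.4 | 86.9 → 92.9 | 86.8 → 90.0 |
| 0.5 | 87.2 → 93.9 | 87.1 → 89.5 | 86.8 → 87.0 |
| 0.7 | 86.8 → 90.8 | 86.9 → 86.5 | 87.0 → 86.1 |
| 0.8 | 86.9 → 89.4 | 86.9 → 85.8 | 87.1 → 87.6 |
| 0.9 | 87.1 → 87.8 | 86.9 → 87.6 | 86.5 → 93.1 |

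Eight of the 15 gain 2.4 to 9.4 points. Seven change by about 1 point or less, three of them losses (−0.4, −1.1, −0.9). At k = 1 the half-widths are 7.8, 8.4, 8.9 and 9.4 points for ρ = 0.3, 0.5, 0.7 and 0.9. The worst case, ρk = 1, run with 80,000 trials, goes from 86.8% to 85.7%, half-width 9.7. If k is below 1 the gain is larger: at k = 0.8, adjusted power is 96.5% to 99.0%.

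**4. The stratum term alone.** The gap in mean change between strata is also an assumption. With overall SD held at 15, the within-stratum SD is √(225 − gap² × p(1 − p)). For a 24/16 split and a 10-point gap this is √(225 − 100 × 0.24) = 14.18.

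| Gap, split | Power, unadjusted → with stratum (%) | Type I error, unadjusted → with stratum (%) |
|---|---|---|
| 5, 24/16 | 87.0 → 87.5 | 4.8 → 5.1 |
| 10, 24/16 | 88.0 → 90.2 | 3.6 → 4.9 |
| 15, 24/16 | 89.7 → 94.2 | 2.5 → 5.1 |
| 10, 20/20 | 88.0 → 90.3 | 3.6 → 4.9 |
| 10, 32/8 | 87.7 → 89.0 | 4.1 → 5.0 |

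The unadjusted test never exceeds 5%, so it is valid, and it becomes conservative as the gap grows. If SD 15 is instead read as the within-stratum SD, with 30% of patients on twice-daily glargine and a 15-point gap, unadjusted power is about 82% and the stratum term restores it to about 87%.

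**5. Precision of the arm-by-stratum contrast.** Half-width = 2.028 × 15 × √(sum of 1/n over the four cells). For 20/20: 2.028 × 15 × √(4/10) = 19.2. For 24/16: 19.6. For 32/8: 24.1 points.

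**The case against.** The strongest reply is that nothing is broken. The change score is deliberate: Section 2 defines the endpoint that way, and Section 3.2 has patients serve as their own controls. The test is valid, the power figure is right, and a definitive comparison is left to a later study. This stands, and it limits the point to an improvement.

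Second, the missing covariates are read from silence. Section 4 names no model, and a simple power calculation does not bind the analysis. This also stands, but it is a reason to write the model down before unblinding rather than leave the choice open.

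Third, the benefit rests on assumed inputs, and a count of 8 out of 15 depends on the grid and is not a probability. That is correct. If spread rises only under direct conversion (k = 1 bridging, 1.5 direct), power moves from 87.0 to 93.1, 87.0 to 89.4, 87.3 to 86.8 and 86.9 to 86.1% at ρ = 0.3, 0.5, 0.7 and 0.8, so there is no gain at the two higher correlations. If exclusions left 14 to 16 analysed per arm (an assumption), the worst-case loss would be about 1.5 to 2 points, and the favourable cases would gain more.

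Fourth, the stratum term matters little unless the gap is large: at 5 points it adds half a point of power, and a 15-point gap equals the whole assumed treatment effect. This is fair. The case for the stratum term rests mainly on analysing as randomised and keeping the test at its nominal level.

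**Conclusion.** The concern holds as a matter of precision. As described, the primary comparison includes neither baseline TIR nor the stratum used to randomise. It remains a valid test, and the 87% power is correct for it.

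Adding both terms would bring the half-width from 9.6 to between 7.8 and 9.4 points at k = 1 and ρ from 0.3 to 0.9. The gain is small or absent when ρk is near 1, where about 1 power point is lost. The potential gain therefore exceeds the potential loss, but a gain is not assured.

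These figures assume normal data, a change SD of 15, all 40 patients analysed, and values of ρ, k, stratum gap and stratum split that the documents do not give. Confidence in the size of the gain is moderate; that the two terms are absent from the plan as written is clear.

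**What to change.** Before unblinding, state in Section 4 that the primary analysis is a linear model of TIR change on randomised arm, baseline 48-hour TIR and glargine-frequency stratum. Report the adjusted arm difference with its 95% CI and p-value, and give the unadjusted difference in mean change as support. Using post-dose TIR as the outcome gives the same arm effect with the opposite sign, because change is defined as before minus after; say which is used.

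Optionally, report the arm-by-stratum contrast with its 95% CI beside the planned same-direction statement, so that readers see how little 40 patients can say about it.

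The cost is a few sentences and no new data. The model uses 2 degrees of freedom, worth about 1 power point (86.8% to 85.7%) if the covariates explain nothing and all 40 patients are analysed.

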982 prescribe patients with glucagon kit to be used for treatment of hypoglycemia as needed.
983 Patients will have access to medical providers at the DCC by phone or e-care
984 communication if additional guidance is needed in the event of overdose by the study drug
985 during the study.

986

987

11. LIABILITY AND SUBJECT INSURANCE:

988

989 During and following a subject's participation in the clinical trial, the investigators and
990 their institution will provide adequate medical care to the study subject for any study-
991 related adverse events, including clinically significant laboratory values related to the
992 study. This medical care for study subjects will be provided regardless of their insurance
993 status.

994

995 The investigators will be responsible for the conduct of the study and agree to defend,
996 indemnify, and hold harmless Novo Nordisk, any of its parent companies, affiliates, or
997 subsidiaries, and their respective officers, directors, employees, agents, representatives,
998 distributors, salespersons, customers, licensees, and end-users from and against any claim,
999 suit, demand, loss, damage, expense or liability imposed by any third party arising from or
1000 related to: (a) any breach of Novo Nordisk-investigators' obligations or representations; or
1001 (b) Novo Nordisk-investigators' negligent or grossly negligent use or willful misuse of the
study drug, the results, or services derived therefrom. This

GLIDE Study

1002 indemnification shall not apply in the event and to the extent that a court of competent
1003 jurisdiction or a duly appointed arbiter determines that such losses or liability arose as a
1004 result of Novo Nordisk's gross negligence, intentional misconduct, or material breach of
1005 its responsibilities.

1006

1007

1008 12. EVALUABILITY OF SUBJECTS:

1009 For all analyses, patients not meeting the compliance criteria of the study listed under
1010 Section 3.13 will not be included in the analyses. Clinician investigators will determine
1011 patients' compliance with study drug based on patient's recorded log and patients' time
1012 spent wearing CGM after CGM data has been downloaded at the follow-up visit. We will
1013 include data from all randomized participants in our data analysis. The subjects or
1014 observations to be excluded, and the reasons for their exclusion will be documented and
1015 signed by the clinician investigators or staff prior to database release. The documentation

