APPENDIX A: Sample Subject Daily Insulin Logbook, version-1.0

1106

Trial ID: U1111-1214-3257

1107

1108

Subject No. XX Subject Initials: ABC Subject DOB: MMDDYY

1109

1110

Date: MMDDYY Study Day: #

Time point	Time (hh:mm)	BG value (mg/dL)	Carbohydrates consumed (grams)	Bolus insulin dose NUTRITIONAL (units)	Bolus insulin dose CORRECTION (units)	Basal insulin dose (units)
Before breakfast						
Before lunch						
Before dinner						
At bedtime						
*Extra time point #1						
*Extra time point #2						
*Extra time point #3						

1111

* To be used only if needed. NOTE: please use these fields to enter any snacks consumed as well.

1112

1113

1114

Did you exercise today? [] yes or [] no

1115

1116

If yes, then please specify when and how long: from _____ to _____ (hh:mm)

1117

1118

1119

1120

1121

1122

1123

1124

1125

1126

1127

1128

1129

1130
1131 **APPENDIX B: Sample Subject Hypoglycemia Episode Form, version 1.0**
1132 (see Section 3.12 for details on directions to fill out this form)
1133
1134 Trial ID: U1111-1214-3257
1135 Subject No. XX Subject Initials: ABC Subject DOB: MMDDYY
1136
1137 Date: MMDDYY Study Day: #
1138
1139 1. When did the low BG start? _____(hh:mm)
1140 2. What was the lowest BG value during the episode? _____(mg/dL)
1141 3. Did you experience any of the following symptoms with this low BG?
1142 [] No or [] Yes (check all that apply)
1143 [] Sweating
1144 [] Trembling
1145 [] Feeling hungry
1146 [] Rapid or irregular heartbeat
1147 [] Feeling confused
1148 [] Feeling drowsy
1149 [] Speech difficulty
1150 [] Visual disturbances
1151 [] Odd behavior
1152 [] Impaired balance
1153 [] Reduced coordination of movements
1154 [] Headache
1155 [] Feeling discomfort or unease
1156 [] Seizure
1157 [] Loss of consciousness
1158 [] Other
1159 4. Were you able to manage it by yourself? [] yes or [] no. If no, please fill out Q9-
1160 12 as well. If yes, please skip Q9-12.
1161 5. How did you treat the low BG? _____
1162 6. When did the low BG resolve? _____(hh:mm)
1163 7. Did this episode happen in relation to physical activity? [] Yes or [] No
1164 If yes, then what were you doing? _____
1165 8. Were you asleep when the low blood glucose happened? [] Yes or [] No
1166 9. Who assisted in treatment of the episode? _____
1167 10. Where was the treatment administered? _____
1168 11. What treatment was provided to treat the episode? _____
1169 12. Were your symptoms alleviated by this treatment? [] Yes or [] No
1170
1171
1172
1173

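### Section 12 both excludes non-compliant patients from every analysis and includes everyone randomised, so the primary analysis set is undefined; 3.8 and 3.10.5 also disagree on replacement.

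*Combined protocol and SAP*

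**What the plan says.** **Analysis set.** Section 12 opens with "For all analyses, patients not meeting the compliance criteria of the study listed under" "Section 3.13 will not be included in the analyses". Two sentences later it says that the study will "include data from all randomized participants in our data analysis". Section 3.8 repeats the inclusive rule. Section 4 describes the comparison of mean change in TIR between randomised arms but does not name the set of patients.

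**Compliance rule.** Section 3.13: "Compliance will be defined by the following (all 3 need to be met to be considered" compliant. The criteria are no missed basal dose, "No missed doses of nutritional insulin with meals", and study CGM wear above 19 hours a day. They cover the 48 hours before and the 48 hours after the first IDeg dose. Under section 12 the clinician investigators judge compliance from the patient's log and the time "spent wearing CGM after CGM data has been downloaded at the follow-up visit". Exclusions are documented and signed before database release.

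**Replacement.** Section 3.8 says that patients who discontinue are not replaced. Section 13 says the same of those who stop study drug or withdraw consent. Section 3.10.5 says that a patient who makes a second transition error is discontinued and replaced if supplies permit.

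**Power.** Section 4: "then 20 patients in each group will provide 630 87% power to observe a statistically significant (at the two-sided level of .05". It assumes a 15-point difference and an SD of 15 points. About 40 patients are to be randomised (3.4), at the end of the screening visit (7.1, footnote c).

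**The concern.** The two rules in section 12 put different patients into the primary comparison, and both stand in the current text. Signing exclusions before database release fixes when they are recorded, not which rule applies.

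The choice matters beyond tidiness. Half of the compliance window lies after the first IDeg dose, so the exclusion reading selects patients on behaviour that treatment may influence. Section 3.1 expects hypoglycaemia, hyperglycaemia and correction boluses to differ by arm, and mealtime dosing could plausibly respond to any of these. If it does, the patients who remain are no longer the groups that randomisation formed. The judgement is also made after the download that holds the primary outcome.

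The replacement clash is smaller. It leaves open how many patients are randomised and whether a replaced patient still counts. Because section 4 names no set, a reader cannot tell whether its 20 per group are randomised patients or compliant ones.

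**Working it through.** **1. The rules side by side**

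| Question | One rule | The other rule |
|---|---|---|
| Is a patient who fails 3.13 analysed? | No, in any analysis (12, first sentence) | Yes (12, third sentence; 3.8) |
| Is a discontinued patient replaced? | No (3.8; 13 within its narrower scope) | Yes, after a second transition error (3.10.5) |

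Sections 3.8 and 13 agree with each other. The direct replacement clash is 3.8 against 3.10.5.

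The inclusive rule cannot be applied literally either. A patient with under 38 hours of usable CGM data at the repeat check is discontinued before any IDeg (3.10.4), so has no after-dose TIR. No handling is given.

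**2. Reproducing the 87%**

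Inputs (section 4): difference 15, SD 15, two-sided alpha 0.05, 20 per arm. Standardised effect = 15/15 = 1.

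Two-sample t-test with noncentrality 1/√(1/n₁ + 1/n₂). For 20 per arm this is 1/√(2/20) = 3.162 on 38 df, and power is 86.9%. The stated 87% is reproduced.

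**3. Power if fewer are analysed** (loss rates are assumptions; equal loss in both arms)

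| Loss | Analysed per arm | Noncentrality √(n/2) | Power |
|---|---|---|---|
| 0% | 20 | 3.162 | 86.9% |
| 5% | 19 | 3.082 | 85.1% |
| 10% | 18 | 3.000 | 83.0% |
| 15% | 17 | 2.915 | 80.7% |
| 20% | 16 | 2.828 | 78.1% |

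If all four losses fall in one arm (20 v 16), power is 82.5%.

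**4. How strict the all-or-none rule is** (illustration)

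The logbook in Appendix A has a "Bolus insulin dose NUTRITIONAL (units") column and rows for three meals: 3 × 4 days = 12 doses in the 96 hours. If each is missed independently with chance p, the share failing this one criterion is 1 − (1 − p)¹²:

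- p = 0.5%: 5.8%, or 2.3 of 40
- p = 1%: 11.4%, or 4.5 of 40
- p = 2%: 21.5%, or 8.6 of 40

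The values of p are assumed. Misses cluster within patients, so for the same p the true shares would be lower.

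**5. Scale of a possible shift** (illustration)

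Suppose a fraction L of one arm is excluded and their mean change differs from that arm's mean by 15 points (1 SD). The remaining mean moves by 15L/(1 − L): 15 × 0.1/0.9 = 1.7 points for 2 of 20, and 15 × 0.2/0.8 = 3.8 points for 4 of 20, against a planned difference of 15. The documents support neither the fraction nor the 1 SD, and the sign could go either way.

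**The case against.** The best defence is that this is a pilot with safeguards. Short baseline CGM data triggers a second collection (3.10.4), a forgotten or wrong transition gets another attempt (3.10.5), and a missed transition alone does not end participation (3.7). The outcome is complete 48 hours after the first dose. Power stays above 80% up to an equal loss of 15%, so the lack of a loss allowance is minor. All of this stands.

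On bias, section 8.5 keeps patients and research staff unaware of assignment, and compliance is judged from the log and wear time rather than from glucose values. Section 3.13 also says that compliance is assessed at the telephone calls. This weakens any suggestion of outcome-driven exclusion. It does not remove the problem, because blinded judgement cannot prevent compliance itself from differing by arm. Nor can the calls settle it: the third is the day after the first dose, and none is scheduled between then and CGM removal, so the full post-dose window is judged later.

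A reader might infer three stronger things that the documents do not support:

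- **That the trial is underpowered or the 87% is wrong.** The figure is right for 20 analysed per arm, and no loss rate is given.
- **That the exclusion favours a particular arm.** Nothing says that patients omit meal doses because of low glucose, and a skipped meal need not count as a missed dose with a meal.
- **That 3.8, 12 and 13 all conflict on replacement.** Section 12 does not address replacement, and 13 agrees with 3.8.

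**Conclusion.** The plan is wrong as written on who is analysed. Section 12 contradicts itself and 3.8, and nothing ranks the rules. This rests on the text alone and needs no assumption. The 3.8 and 3.10.5 clash on replacement is equally plain but matters less.

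That the exclusion reading can make the arms unlike follows from its use of post-dose behaviour. The direction and size cannot be derived from the documents; the shifts of 1.7 and 3.8 points only show what assumed inputs would imply. The effect on power is modest: 83.0% at an assumed 10% loss and 78.1% at 20%. It should be fixed because the pilot's data are meant to inform the design of a larger study (section 4), and that use needs a defined population.

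**What to change.** 1. **Section 12 (and 3.8, 4).** Remove the exclusion sentence for the primary analysis. Define the primary set as all randomised patients who took the first IDeg dose, analysed as randomised whatever their 3.13 compliance, with TIR from the available CGM data in both 48-hour windows. State one minimum of usable data for both windows. The 38 hours already used at baseline is an example, and it matches the wear criterion (2 × 19 = 38). Report by arm every randomised patient without a TIR change, with the reason. Make the 3.13-compliant set a sensitivity analysis.
2. **Sections 3.8 and 3.10.5.** Reconcile them into one replacement rule. If replacement is kept, state that the replaced patient stays in the randomised set.
3. **Section 4.** Add one sentence: the 87% applies to 20 analysed per arm and would be 83% with 18 and 78% with 16 (10% and 20% loss, assumed rates).

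**Cost.** Wording only, with no new visits or data. Keeping non-compliant patients may dilute the difference. In the extreme case where 10% of each arm are non-compliant and show no treatment difference at all, the expected difference falls to 15 × 0.9 = 13.5 points and power with 20 per arm to 79.2%, against 83.0% if they are dropped. One missed meal dose would hardly erase the whole effect, so the real cost should be smaller. A post-dose data minimum is itself a post-dose restriction, which is why losses must be shown by arm.

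Leaving out patients lost before IDeg is safe only if assignment is concealed until then. Section 8.2 can be read as having research staff notified of assignment, while 8.5 says that they are unaware. Those passages should be reconciled as a separate point.
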